7.2 Participant Withdrawal From the Study

A participant must be withdrawn from the study if the participant or participant's legally acceptable representative withdraws consent from the study.

If a participant withdraws from the study, they will no longer receive study intervention or be followed at scheduled protocol visits.

Specific details regarding procedures to be performed at the time of withdrawal from the study, as well as specific details regarding withdrawal from FBR, are outlined in Section 8.1.9. The procedures to be performed should a participant repeatedly fail to return for scheduled visits and/or if the study site is unable to contact the participant are outlined in Section 7.3.

7.3 Lost to Follow-up

If a participant fails to return to the clinic for a required study visit and/or if the site is unable to contact the participant, the following procedures are to be performed:

- The site must attempt to contact the participant and reschedule the missed visit. If the participant is contacted, the participant should be counseled on the importance of maintaining the protocol-specified visit schedule.
- The investigator or designee must make every effort to regain contact with the participant at each missed visit (eg, telephone calls and/or a certified letter to the participant's last known mailing address or locally equivalent methods). These contact attempts should be documented in the participant's medical record.
- Note: A participant is not considered lost to follow-up until the last scheduled visit for the individual participant. The missing data for the participant will be managed via the prespecified statistical data handling and analysis guidelines.
8 STUDY ASSESSMENTS AND PROCEDURES

- Study procedures and their timing are summarized in the SoA.
- Adherence to the study design requirements, including those specified in the SoA, is essential and required for study conduct.
- The investigator is responsible for ensuring that procedures are conducted by appropriately qualified (by education, training, and experience) staff. Delegation of study-site personnel responsibilities will be documented in the Investigator Trial File Binder (or equivalent).
- All study-related medical decisions must be made by an investigator who is a qualified physician.
- All screening evaluations must be completed and reviewed to confirm that potential participants meet all eligibility criteria. The investigator will maintain a screening log to record details of all participants screened and to confirm eligibility or record reasons for screening failure, as applicable.
- Procedures conducted as part of the participant's routine clinical management (eg, blood count) and obtained before providing documented informed consent may be used for screening or baseline purposes provided the procedures meet the protocol-specified criteria and were performed within the time frame defined in the SoA.
- Additional evaluations/testing may be deemed necessary by the investigator and or the Sponsor for reasons related to participant safety. In some cases, such evaluation/testing may be potentially sensitive in nature (eg, HIV, hepatitis C), and thus local regulations may require that additional informed consent be obtained from the participant. In these cases, such evaluations/testing will be performed in accordance with those regulations.
- The maximum amount of blood collected from each participant over the duration of the study is described in operations/laboratory manual.
- Repeat or unscheduled samples may be taken for safety reasons or for technical issues with the samples.

8.1 Administrative and General Procedures

8.1.1 Informed Consent

The investigator or medically qualified designee (consistent with local requirements) must obtain documented informed consent from each potential participant (or their legally acceptable representative) prior to participating in this clinical study or FBR. If there are changes to the participant's status during the study (eg, health or age of majority requirements), the investigator or medically qualified designee must ensure the appropriate documented informed consent is in place.

8.1.1.1 General Informed Consent

Informed consent given by the participant or their legally acceptable representative must be documented on a consent form. The form must include the study protocol number, study protocol title, dated signature, and agreement of the participant (or his/her legally acceptable representative) and of the person conducting the consent discussion.

A copy of the signed and dated informed consent form should be given to the participant (or their legally acceptable representative) before participation in the study.

The initial ICF, any subsequent revised ICF, and any written information provided to the participant must receive the IRB/IEC's approval/favorable opinion in advance of use. The participant or his/her legally acceptable representative should be informed in a timely manner if new information becomes available that may be relevant to the participant's willingness to continue participation in the study. The communication of this information will be provided and documented via a revised consent form or addendum to the original consent form that captures the participant's or the participant's legally acceptable representative's dated signature.

Specifics about the study and the study population are to be included in the study informed consent form.

Informed consent will adhere to IRB/IEC requirements, applicable laws and regulations, and Sponsor requirements.

8.1.1.2 Consent and Collection of Specimens for Future Biomedical Research

The investigator or medically qualified designee will explain the FBR consent to the participant, or the participant's legally acceptable representative, answer all of his/her questions, and obtain documented informed consent before performing any procedure related to FBR. A copy of the informed consent will be given to the participant before performing any procedure related to FBR.

8.1.2 Inclusion/Exclusion Criteria

All inclusion and exclusion criteria will be reviewed by the investigator, who is a qualified physician, to ensure that the participant qualifies for the study.

8.1.3 Participant Identification Card

All participants will be given a participant identification card identifying them as participants in a research study. The card will contain study-site contact information (including direct telephone numbers) to be used in the event of an emergency. The investigator or qualified designee will provide the participant with a participant identification card immediately after the participant provides documented informed consent. At the time of intervention allocation/randomization, site personnel will add the treatment/randomization number to the participant identification card.

The participant ID card also contains contact information for the emergency unblinding call center so that a health care provider can obtain information about study intervention in emergency situations where the investigator is not available.

8.1.4 Medical History

A medical history will be obtained by the investigator or qualified designee. The medical history will collect all active conditions and any condition diagnosed within the prior 10 years that the investigator considers to be clinically important. Details regarding the disease for which the participant has enrolled in this study will be recorded separately and not listed as medical history.

The medical history must include documentation of the reason(s) the participant is undergoing definitive SBRT instead of surgery, as determined by the site's multidisciplinary tumor board. If there is no tumor board, then this decision will be made by the investigator in consultation with a thoracic surgeon and a radiation oncologist if the investigator is not a radiation oncologist. This documentation will be kept with the participant's study records.

If the participant is considered medically inoperable due to one or more comorbidities, these comorbidity(ies) should be included in the participant's study records. Reasons a participant may be considered medically inoperable include, but are not limited to, a history of poor pulmonary function, heart disease, diabetes, vascular disease, or a combination of several unrelated comorbidities that, taken together, contribute to the decision that the participant is not suitable for surgery.

If the participant's tumor is in an anatomically unresectable location, this should be documented in the medical history as the reason the participant is considered inoperable. If the participant has refused surgery, this must also be documented clearly at site as part of the participant's medical history.

To ensure the ethical inclusion of prospective participants with medically operable NSCLC without any undue coercion, these participants will be clearly informed of the advantages of surgery and be sufficiently aware that surgical resection is the preferred treatment for early-stage NSCLC. This discussion occurs prior to providing the participant with any information regarding the KEYNOTE-867 study and in advance of any offer to be screened for enrollment in the study. Thus, the participant's election to forego surgery will be a well-informed decision, made in advance of and with no specific knowledge of the KEYNOTE-867 study, so that inclusion in the study would not impact the opportunity for decision to undergo surgery.

8.1.5 **Prior and Concomitant Medications Review**

8.1.5.1 **Prior Medications**

The investigator or qualified designee will review prior medication use, including any protocol-specified washout requirement, and record prior medication taken by the participant within 42 days before starting the study. Treatment for the disease for which the participant has enrolled in this study will be recorded separately and not listed as a prior medication.

8.1.5.2 Concomitant Medications

The investigator or qualified designee will record medication, if any, taken by the participant during the study through the Safety Follow-up Visit.

8.1.6 Assignment of Screening Number

All consented participants will be given a unique screening number that will be used to identify the participant for all procedures that occur before randomization. Each participant will be assigned only 1 screening number. Screening numbers must not be reused for different participants.

Any participant who is screened multiple times will retain the original screening number assigned at the initial Screening Visit. Specific details on the screening/rescreening visit requirements are provided in Section 8.11.1.

8.1.7 Assignment of Treatment/Randomization Number

All eligible participants will be randomly allocated and will receive a randomization number. The randomization number identifies the participant for all procedures occurring after randomization. Once a randomization number is assigned to a participant, it can never be reassigned to another participant.

A single participant cannot be assigned more than 1 randomization number.

Trial treatment should begin on the day of randomization or as close as possible to the date on which the participant is allocated/assigned.

8.1.8 Study Intervention Administration

Administration of study medication will be witnessed by the investigator and/or study staff.

8.1.8.1 Timing of Dose Administration

8.1.8.1.1 Pembrolizumab or Matching Placebo

Pembrolizumab will be administered as a dose of 200 mg using a 30-minute IV infusion Q3W. Sites should make every effort to target infusion timing to be as close to 30 minutes as possible. However, given the variability of infusion pumps from site to site, a window of -5 minutes and +10 minutes is permitted (ie, infusion time is 30 minutes -5 min/+10 min).

The Pharmacy Manual contains specific instructions for pembrolizumab reconstitution, preparation of the infusion fluid, and administration of infusion solution. Pembrolizumab will be prepared by the unblinded pharmacist and will be dispensed by the blinded pharmacist and administered by blinded and qualified trial site personnel.

The placebo will be a normal saline solution prepared by the unblinded pharmacist. The placebo will be dispensed by the blinded pharmacist and administered by blinded and

qualified trial site personnel in the same manner as the investigational product (pembrolizumab).

The first dose of pembrolizumab or placebo should be administered prior to start of SBRT.

8.1.8.1.2 Stereotactic Body Radiotherapy

Radiotherapy will be administered in 3 fractions totaling 45-60 Gy (preferred regimen), 4 fractions totaling 48-50 Gy, or 5 fractions totaling 50-55 Gy (acceptable regimens) for peripheral tumors, 4 fractions totaling 48-50 Gy or 5 fractions totaling 50-55 Gy for tumors abutting the chest wall, and 5 fractions totaling 50-55 Gy or 8 fractions totaling 60-70 Gy for central tumors, defined as within 2 cm of the proximal bronchial tree and/or abutting the mediastinal pleural. Ultra-centrally located tumors, defined as tumors whose PTV directly contacts or overlaps the proximal bronchial tree, trachea, mainstem bronchus, esophagus, pulmonary vein, or pulmonary artery are not appropriate for SBRT and are excluded from enrollment in this study.

SBRT will be administered preferably starting on C1D1, following administration of pembrolizumab/placebo. There is an allowed window of +7 days to begin SBRT treatment (SBRT treatment must begin between C1D1 and C1D8, inclusive). SBRT will be administered over no more than 2 weeks.

Center credentialing for radiotherapy will be performed according to criteria defined in the Radiotherapy QA manual. Participating institutions must comply with the radiation therapy quality assurance (RT QA) requirements and procedures described in the Radiotherapy QA manual. Sites that do not conform to the requirements of the credentialing will not be allowed to participate.

8.1.9 Discontinuation and Withdrawal

Participants who discontinue study intervention before completion of the treatment period should be encouraged to continue to be followed for all remaining study visits as outlined in the SoA and Section 8.11.2.

Participants who withdraw from the study should be encouraged to complete all applicable activities scheduled for the final study visit should be performed at the time of withdrawal. Any AEs that are present at the time of withdrawal should be followed in accordance with the safety requirements outlined in Section 8.4.

8.1.9.1 Withdrawal From Future Biomedical Research

Participants may withdraw their consent for FBR. Participants may withdraw consent at any time by contacting the study investigator. If medical records for the study are still available, the investigator will contact the Sponsor using the designated mailbox ([contact]). Subsequently, the participant's consent for FBR will be withdrawn. A letter will be sent from the Sponsor to the investigator confirming the withdrawal. It is the responsibility of the investigator to inform the participant of completion of withdrawal. Any analyses in progress at the time of request for withdrawal or

already performed before the request being received by the Sponsor will continue to be used as part of the overall research study data and results. No new analyses would be generated after the request is received.

If the medical records for the study are no longer available (eg, if the investigator is no longer required by regulatory authorities to retain the study records) or the specimens have been completely anonymized, there will no longer be a link between the participant's personal information and their specimens. In this situation, the request for specimen withdrawal cannot be processed.

8.1.10 Participant Blinding/Unblinding

STUDY INTERVENTION IDENTIFICATION INFORMATION IS TO BE UNMASKED ONLY IF NECESSARY FOR THE WELFARE OF THE PARTICIPANT. EVERY EFFORT SHOULD BE MADE NOT TO UNBLIND.

For emergency situations where the investigator or medically qualified designee (consistent with local requirements) needs to identify the intervention used by a participant and/or the dosage administered, he/she will contact the emergency unblinding call center by telephone and make a request for emergency unblinding. As requested by the investigator or medically qualified designee, the emergency unblinding call center will provide the information to him/her promptly and report unblinding to the Sponsor. Before contacting the emergency unblinding call center to request unblinding of a participant's intervention assignment, the investigator who is a qualified physician should make reasonable attempts to enter the toxicity grade of the AEs observed, the relation to study intervention, the reason thereof, etc, in the medical record. If it is not possible to record this assessment in the medical record before the unblinding should not be delayed.

If unblinding has occurred, the circumstances around the unblinding (eg, date, reason, and person performing the unblinding) must be documented promptly, and the Sponsor Clinical Director notified as soon as possible.

For studies that require nonemergency unblinding as part of the study design (eg, disease progression) to support treatment decisions, instructions in the Procedures Manual should be followed. The emergency unblinding center should not be used for this purpose.

Once an emergency unblinding or a nonemergency unblinding that is part of the study design has taken place, the investigator, site personnel, and Sponsor personnel may be unblinded so that the appropriate follow-up medical care can be provided to the participant.

8.1.11 Calibration of Equipment

The investigator or qualified designee has the responsibility to ensure that any device or instrument used for a clinical evaluation/test during a clinical study that provides information about inclusion/exclusion criteria and/or safety or efficacy parameters shall be suitably calibrated and/or maintained to ensure that the data obtained are reliable and/or reproducible. Documentation of equipment calibration must be retained as source documentation at the study site.

8.2 Efficacy Assessments

8.2.1 Tumor Imaging and Assessment of Disease

As of Amendment 08: Central tumor response assessments will be discontinued. Imaging scans will no longer be submitted to iCRO nor read by BICR. Tumor imaging, biopsies, and disease management should be performed per local SOC and Investigator's discretion. The subsections below are retained for reference.

The process for image collection and transmission to the central imaging vendor can be found in the Site Imaging Manual. Screening imaging must also be submitted to the radiation therapy quality assurance vendor as part of the radiation treatment plan approval process; details of this process are found in the RT QA manual. The same imaging technique regarding modality and use of contrast should be used consistently throughout the study. The imaging schedule should follow calendar days and should not be adjusted for cycle delays.

Screening imaging:

• CT with IV and oral contrast (preferred) of the chest and abdomen for all participants, or non-contrast CT of the chest and magnetic resonance imaging (MRI) of the abdomen with IV gadolinium for participants in whom iodinated contrast is contraindicated. Additional anatomy (eg, pelvis/brain) should be captured as clinically indicated. A whole-body fluorodeoxyglucose-positron emission tomography (FDG-PET) scan should also be performed.

Post allocation imaging:

• CT of the chest and abdomen, consistent with the method used at screening. Additional anatomy (pelvis/brain/extremity/etc.) should be captured as clinically indicated.

Local site investigator/radiology assessment of PET imaging to confirm staging (T1 or 2, N0, M0) will be used to determine participant eligibility. All scheduled images for all study participants from the sites will be submitted to the central imaging vendor. In addition, all other imaging (including all modalities and anatomies) obtained at an unscheduled time point to determine disease recurrence, as well as supplemental imaging obtained for other reasons that captures radiologic recurrence, must be submitted to the central imaging vendor.

8.2.1.1 Initial Tumor Scans

Initial tumor imaging (whole-body FDG-PET and CT of chest and abdomen) at screening must be performed within 42 days prior to the date of randomization. The site investigator/local radiology reviewer must review screening images to confirm the participant has no nodal or metastatic involvement. The screening images must be submitted to the central imaging vendor for retrospective review. This scan is considered the reference point for regional or distant recurrence on study.

Tumor imaging via PET/CT performed as part of routine clinical management (prior to documented informed consent signature) is acceptable for use as screening tumor imaging if the CT portion is of diagnostic quality, is performed within 42 days prior to the date of randomization and can be assessed by the central imaging vendor retrospectively.

8.2.1.2 Tumor Scans During the Study

The first scheduled post randomization imaging assessment (chest and abdomen CT) should be performed at 12 weeks (\pm 7 days) from the date of randomization (at least 10 weeks post completion of SBRT). This scan is considered the reference point for monitoring local recurrence (see Section 8.2.1.3), however, unscheduled imaging due to new clinical symptoms can occur at any time, including prior to the Week 12 assessment, to identify either new metastatic/regional disease or recurrence of local treated disease. Subsequent tumor imaging should be performed every 16 weeks (Q16W \pm 7 days) until 156 weeks post-randomization; and every 6 months (Q6M \pm 14 days) thereafter [Schneider, B. J., et al 2019]. Images will continue to be obtained (Q6M \pm 14 days) even after initiating the new anticancer therapy if recurrence has not been document or verified by BICR.

Timing of tumor imaging should follow calendar days and should not be adjusted for delays in cycle starts. (Note: the date imaging is performed is the date of assessment, not the date the images are reviewed.) Imaging should continue to be performed until disease recurrence as assessed by local investigator/radiologist, withdrawal of consent, pregnancy, loss to follow-up, or death, whichever occurs first. Supplemental imaging must be submitted to the central imaging vendor if it shows evidence of recurrence.

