	After a Screening phase of up to 42 days, each participant will be randomized to receive study intervention until disease recurrence is documented, unacceptable adverse events, intercurrent illness that prevents further administration of treatment, death from any cause, investigator decision, participant decision, or withdrawal of consent, or until the participant has received 17 administrations of pembrolizumab or placebo (approximately 1 year).
	After the end-of-treatment, each participant will be followed for the occurrence of AEs and spontaneously reported pregnancy as described in Section 8.4.
	Participants who discontinue treatment for reasons other than documented disease recurrence, or recurrence has not been verified by Blinded Independent Central Review (BICR), will have posttreatment follow-up imaging for disease status until disease recurrence is documented radiographically and verified by BICR, withdrawing consent, pregnancy, death, or loss to follow-up, whichever occurs first. Images will also continue to be obtained after initiating the new anticancer therapy if recurrence has not been documented or verified by BICR. All participants will be followed by telephone for OS until death, withdrawal of consent, or the end of the study.
	Upon study completion, participants are discontinued and may be enrolled in a pembrolizumab extension study, if available.

Confidential

Study Governance Committees:

Executive Oversight Committee	Yes
Data Monitoring Committee	Yes
Clinical Adjudication Committee	No
Steering Committee	No

Study governance considerations are outlined in Appendix 1.

As of Amendment 08, the Executive Oversight Committee and Data Monitoring Committee are no longer applicable as outlined 10.1.4.1 and 10.1.4.2.

Study Accepts Healthy Participants:

No

A list of abbreviations used in this document can be found in Appendix 10.

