1.3 Schedule of Activities (SoA)

Table 1 Study Schedule of Activities: Pembrolizumab & SBRT Treatment

As of Amendment 08, information regarding ePRO assessments (EORTC QLQ-C30, EORTC QLQ-LC13, and EuroQoL EQ-5D-5L), biomarker samples (blood for genetic analysis, blood for ctDNA analysis, optional tumor sample), biopsies, and tumor imaging for BICR will no longer be collected. Tumor imaging, biopsies, and disease management should be performed per local SOC and Investigator's discretion. Efficacy data collection, including Follow-up and Survival Follow-up visits for efficacy will no longer be conducted. Safety reporting for AEs and SAEs must adhere to time windows per protocol. Updated analyses are described in Section 9.

Study Period	Screening Phase	Treatment/Intervention (3-week cycles)			EOT	Posttreatment			Notes	
Visit Number/Title	Screening	Cycle 1	Cycle 2	Cycle 3	Cycle 4 onward	DC	Safety FU	FU Visits	Survival FU	
Scheduling window (days)	-42 to -1	+3	±3	±3	±3	At time of DC + 7 days	30 days from last dose + 14 days	Q16W ^a (±7 days)	Q12W (±7 days)	
Administrative Procedu	ures						· ·			·
Informed Consent	Х									
Informed Consent for Future Biomedical Research	Х									FBR consent is optional.
Inclusion/Exclusion Criteria	Х									
Participant Identification Card	Х									
Medical/Surgical History	Х									
Prior/Concomitant Medication Review	Х	x	Х	х	Х	X	Х	X		Prior and concomitant medications should be tracked from Day -42 forward.
Intervention (Randomization)	Х									
Subsequent Antineoplastic Therapy Status						X	X	X	Х	

Study Period	Screening Phase	Treatm (3-wee	ent/Interve k cycles)	ntion		EOT	Posttreatment			Notes
Visit Number/Title	Screening	Cycle 1	Cycle 2	Cycle 3	Cycle 4 onward	DC	Safety FU	FU Visits	Survival FU	
Scheduling window (days)	-42 to -1	+3	±3	±3	±3	At time of DC + 7 days	30 days from last dose + 14 days	Q16W ^a (±7 days)	Q12W (±7 days)	
Survival Status			←=-				→		х	After investigator- determined recurrence or start of new anticancer treatment. In addition, upon Sponsor request, participants may be contacted for survival status at any time during the course of the study.
Study Drug Administra	ation	•								·
Pembrolizumab or Placebo		X	Х	х	Х					Maximum of 17 total cycles.
SBRT		x								Administered over a maximum 2-week interval, concurrent with Cycle 1. Preferably starting on C1D1 with a +7-day window allowed (up to C1D8 inclusive) following pembrolizumab/placebo administration.
Safety Procedures						-				

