8.2.1.5 End-of-treatment and Follow-up Tumor Scans

If participants discontinue study intervention, tumor scans should be performed at the time of discontinuation (\pm 4-week window) unless previous scans were obtained within 4 weeks of discontinuation. If participants discontinue study intervention due to documented disease recurrence, this is the final required tumor scan.

If participants discontinue study intervention without documented disease progression, every effort is to be made to monitor disease status by acquiring tumor scans using the same schedule calculated from the date of [randomization/allocation], refer to Section 8.2.1.2.

Scans are to be continued until one of the following conditions are met:

- Disease progression as defined by RECIST 1.1 verified by BICR
- Pregnancy
- Death
- Withdrawal of consent
- The end of the study

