8.11.4.3 Survival Follow-up

Participants who experience confirmed disease recurrence will move into the Survival Follow-up Phase and should be contacted by telephone approximately every 12 weeks to assess for survival status until death, withdrawal of consent, or the end of the study, whichever occurs first.

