9.6.1 Statistical Methods for Efficacy Analyses

9.6.1.1 Event-free Survival (EFS)

The non-parametric Kaplan-Meier method will be used to estimate the EFS curve in each treatment group. The treatment difference in EFS will be assessed by the stratified log-rank test. A stratified Cox proportional hazard model with Efron's method of tie handling will be used to assess the magnitude of the treatment difference (ie, HR) between the treatment arms. The HR and its 95% CI from the stratified Cox model with Efron's method of tie handling and with a single treatment covariate will be reported. The stratification factors used for randomization (see Section 6.3.2) will be applied to both the stratified log-rank test and the stratified Cox model.

Since disease recurrence is assessed periodically, recurrence can occur any time in the time interval between the last assessment where an event was not documented and the assessment when an event is documented. For the primary EFS analysis, the true date of recurrence will be approximated by the date of the first assessment at which an event is objectively documented, regardless of discontinuation of study medicine or missed study visits. Death is always considered as a confirmed EFS event. Participants who do not experience an EFS event will be censored at the last disease assessment (Table 7). Sensitivity analyses may be conducted using different censoring rules and will be documented in the sSAP as needed.

Situation	Primary Analysis	
Recurrence, or death documented; ≤1 missed disease assessment; and event is before new anti-cancer treatment initiation, if any	EFS event at date of documented recurrence, or death	
Recurrence or death documented; either immediately after having ≥ 2 consecutive missed disease assessments or event is after new anti-cancer treatment initiation, if any	EFS event at date of documented recurrence, or death	
No recurrence and no death; and new anti-cancer treatment is not initiated	Censored at last disease assessment	
No recurrence and no death; new anti-cancer treatment is initiated	Censored at last disease assessment	

Table 7	Censoring	Rules for	Primary	Analysis	of EFS
1.0010 /		1.00100 101		1 111001 5 010	01 D 1 N

If the proportional hazards assumption is not valid, supportive analyses using RMST method [Uno, H., et al 2014] may be conducted for EFS to account for the possible non-proportional hazards effect.

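### Does the sentence in 8.2.1.2 that ends imaging at locally assessed recurrence bias EFS through informative censoring?

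*Combined protocol and SAP*

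**What the plan says.** Section 8.2.1.2 contains the sentence at issue: "Imaging should continue to be performed until disease recurrence as assessed by local investigator/radiologist", or until withdrawal of consent, pregnancy, loss to follow-up or death. The Synopsis (1.1) states a different rule: participants who stop treatment without verified recurrence "will have posttreatment follow-up imaging for disease status until disease recurrence is documented radiographically and verified by BICR". Sections 4.1 and 7.1 agree with the Synopsis, and the list of stopping conditions in 8.2.1.5 has "Disease progression as defined by RECIST 1.1 verified by BICR".

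Two other places are loosely worded. Section 8.2.1.5 also says: "If participants discontinue study intervention due to documented disease recurrence, this is the final required tumor scan". The survival-status note in the Schedule of Activities (1.3) reads "After investigator- determined recurrence or start of new anticancer treatment", while 8.11.4.3 says "Participants who experience confirmed disease recurrence will move into the Survival Follow-up Phase".

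On the analysis side, 9.4.1.1 counts recurrence by BICR, by positive local pathology, or by physical examination confirmed by either. Under 9.6.1.1 and Table 7, every death is an event, and "Participants who do not experience an EFS event will be censored at the last disease assessment".

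**The concern.** The endpoint depends on central reading, but this sentence lets the site's reading end the scans. Suppose a site calls recurrence, no biopsy is taken, central review does not verify the call, and scanning stops. A participant who is still alive is then censored at the last scan, which is the scan that raised the suspicion. That censoring depends on the outcome and makes EFS look better than it is. If it happened more often in one arm, the hazard ratio would be biased as well. Disagreement is plausible: 8.2.1.1 to 8.2.1.3 rely on CT after radiotherapy, and 8.2.1.3.1 warns that tissue effects of SBRT complicate the local assessment. Interim analysis 1 (IA1, cutoff 11-JUN-2024) is the only EFS analysis, so later scans cannot repair it.

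**Working it through.** **1. Which rule governs an unverified site call?**

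- Section 8.2.1.2, the sentence at issue: read alone, stop.
- Section 8.2.1.2, preceding paragraph: continue after new anticancer therapy if central review has not verified recurrence.
- Sections 1.1, 4.1, 7.1 and the 8.2.1.5 list: continue until central verification. Section 7.1 exempts pathologically confirmed recurrence and refers to 8.2.1.4 by number.
- Section 8.2.1.4: written for this exact case. The participant remains on study and the next scan is resubmitted.
- Section 8.2.1.3 and the Schedule of Activities: where biopsy is not appropriate, a confirmation scan follows (at least 4 weeks later, or 4 to 6 weeks later).
- Sections 8.2.1 and 8.2.1.2: unscheduled imaging done to determine recurrence, and supplemental imaging that shows it, must go to the central vendor.

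One general sentence stands against a specific procedure and several consistent statements.

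**2. Who could be lost?** Only a participant for whom all of these hold: true recurrence; no positive biopsy; not verified centrally, even on the confirmation scan; scans stopped despite 8.2.1.4; no later submitted image that central review verifies; alive at the cutoff.

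**3. How many?** The plan gives no rate of site-central disagreement. The design inputs behind 436 are not visible, so 436 is taken as given. The anchor for events is the phase 2 study described in 2.2.4 (4-year EFS 53% and 77%; its EFS also counts second primary lung cancers).

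- Events with that study's effect: 218 × 0.47 + 218 × 0.23 = 152.6.
- Events with 53% in both arms: 436 × 0.47 = 204.9.
- Midpoint: 178.8.

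Assumed central values: 60% of events are recurrences, 40% have no biopsy, 20% of those are unverified, 50% of unverified calls are true, 65% are alive at cutoff.

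- All sites follow the sentence: 178.8 × 0.6 × 0.4 × 0.2 × 0.5 × 0.65 = 2.8.
- A quarter do: 2.8 × 0.25 = 0.7.

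The ranges used were recurrence 50–70%, no biopsy 30–50%, unverified 10–30%, true 30–70%, sentence followed 10–100%, alive 50–80%. Drawing each uniformly gives a median of 1.3 (5th to 95th percentile 0.3 to 3.6). The corner extremes are about 0 and 12.

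**4. What would it do to EFS?** A simulation used the control hazard −ln(0.53)/4 = 0.159 per year and the protocol's scan schedule. Its assumptions were: 60% of first events recurrence; half of site calls biopsied; a confirmation scan for the rest; a 0.5 chance of verification at that scan and at each later one; death rate 0.35 per year after recurrence; follow-up uniform from 0.25 to 5 years. It treats every site call as a true recurrence and allows no verification once scans stop.

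| Unbiopsied calls initially unverified | Censored of 436, all sites follow the sentence | 3-year control EFS overstated (points) | Censored if scans stop in a quarter of exposed participants |
|---|---|---|---|
| 10% | 1.1 | 0.2 | 0.3 |
| 20% | 2.1 | 0.4 | 0.5 |
| 30% | 3.2 | 0.6 | 0.8 |

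In the quarter case the overstatement is at most 0.14 points. With all sites following the sentence, the hazard ratio moves by about 0.001 when the unverified share is equal in both arms, and by 0.006 to 0.008 when it is 15% in one arm and 30% in the other.

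A cruder bound puts three lost events in one arm. With 179 events split evenly, a hazard ratio of 1.00 becomes 86.5/89.5 = 0.97 or 89.5/86.5 = 1.03.

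**5. Would an analysis counting the local calls help?** It would also count false-positive calls. If those occur in 1.4% of one arm and 2.9% of the other (0.014 × 218 = 3 participants against 0.029 × 218 = 6), a true hazard ratio of 1.00 becomes about 1.02 with biopsy-negative cases excluded, and about 1.04 without that exclusion. Either shift exceeds the 0.006 to 0.008 at issue.

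**The case for a change.** The contradiction is real. For an unbiopsied, unverified site call, a site cannot obey both this sentence and 8.2.1.4, and the censoring follows directly from Table 7. Keeping the section for reference does not erase its effect on data collected up to the IA1 cutoff. Losses would also be larger if sites skipped other steps. In the same simulation with no confirmation scan, 2, 4 or 6 participants are censored at 10%, 20% or 30% unverified; with no biopsy either, 4, 8 or 12, overstating EFS by up to 2.4 points. A by-arm count of unverified, unbiopsied site calls would replace these assumptions with a fact at little cost.

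The contradiction stands as a matter of wording. The larger counts do not describe this plan, because they require sites to ignore the biopsy and confirmation-scan steps as well as 8.2.1.4. The two looser passages add little. The survival-status note says when survival status is collected, not that scans stop, and the word documented in 8.2.1.5 sits above a list that requires central verification. A count would be informative, but it is descriptive and alters no planned result.

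**Conclusion.** This is a clerical inconsistency and calls for no change to the plan. The intended rule, imaging until central verification, is stated repeatedly, and 8.2.1.4 settles the disputed case. The likely loss runs from under one to about three participants of 436, and the simulated shift in the hazard ratio is at most 0.008 even if every site follows the sentence. Apart from 436 and the 53% and 77% anchors, every input is assumed, and nothing in the documents shows that any participant was lost. A material difference between arms is not expected, since sites (6.3.3) and central radiologists (9.2) were blinded. OS does not depend on scans.

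Rewording would alter nothing now: under Amendment 08 central reads have ended and 8.2.1 is retained for reference. On the analysis side, 9.6.1.1 already says: "Sensitivity analyses may be conducted using different censoring rules and will be documented in the sSAP as needed". The supplemental SAP is not among the documents, so such a run may already be there. Making it mandatory could add more bias than it removes. If the IA1 report is being prepared, a by-arm count of site-called recurrences that were neither centrally verified nor biopsy-positive is a reasonable optional addition.
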